### 4.7.3 Secondary Efficacy Variables

Secondary efficacy endpoints are:

- The incidence of infections other than acute serious bacterial infections meeting FDA guidance criteria.
- The number of days missed from work/school/kindergarten/day care or days unable to perform normal daily activities due to infections.
- The number of days that the care provider of the pediatric subject had to miss work in order to care for the child due to infections.
- The number of days of unscheduled physician visits due to infections.
- The number of days of hospitalizations due to infections.
- The number of days of IV therapeutic antibiotics.
- The number of days of oral (PO) therapeutic antibiotics.
- Time to resolution of infections.
- The incidence of infections other than serious bacterial infections by trough IgG levels. The categories of trough IgG levels will be determined by looking at the distribution of trough IgG levels at the study completion. Incidence will be summarized by total group mean of trough IgG level throughout treatment, including the trough IgG level from infusion 1 to follow up assessment ( $<$  mean Trough IgG,  $\geq$  mean Trough IgG).

These endpoints will be analyzed descriptively by infusion schedule and overall based on ITT and PP populations, respectively. Subject with no experience of specific event will be included in the analysis as zero incidence, zero day, or zero time duration. For hospitalizations, the number and (total) duration for each subject will be calculated and converted to a figure per year. These data will be presented using the standard set of summary statistics (except that the mean and SD will be calculated weighting for the duration of data available for each subject).

Infections is defined as TEAE coded to MedDRA system organ class ‘Infections and infestations’, or otherwise suggestive of an infection by medical review.

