## 2.2 Secondary Efficacy Endpoints/Variables

- The incidence of infections other than acute serious bacterial infections meeting FDA guidance criteria.
- The number of days missed from work/school/kindergarten/daycare or days unable to perform normal daily activities due to infections.
- The number of days that the care provider of the pediatric subject had to miss work in order to care for the child due to infections.
- The number of days of unscheduled physician visits due to infections.
- The number of days of hospitalizations due to infections.
- The number of days of IV therapeutic antibiotics.
- The number of days of oral (PO) therapeutic antibiotics.
- Time to resolution of infections.
- The incidence of infections other than serious bacterial infections by trough IgG levels.

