## 2.5 Primary Pharmacokinetic Endpoints/Variables

- Pharmacokinetic parameters of total IgG (assessed in PK population).

- Trough serum total IgG levels before each infusion of GC5107 in all subjects and the interval between infusions will be recorded.

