## 3 INVESTIGATIONAL PLAN

This will be a prospective, open-label, single-arm, multicenter, historically controlled, Phase III study measuring the safety, efficacy, PK, and tolerability of GC5107 in subjects with PHID.

- The study design is an open-label, uncontrolled study of at least 26 adult subjects, at least 8 adolescent subjects aged  $\geq 12$  to  $< 17$  years and at least 8 child subjects aged  $\geq 2$  to  $< 12$  years with well-defined PHID.
- To guard against dropout and to assure more than adequate power, up to 50 subjects will be enrolled.
- All subjects will be followed for 12 months during which infusions will be given every 21 or 28 days.
- To demonstrate efficacy, the serious bacterial infection rate will be required to have an upper one-sided 99% confidence limit less than 1.0 per subject per year.
- Pharmacokinetics will be determined after the 5th study infusion.

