## 4.7 Efficacy Evaluation

### 4.7.1 Analysis and Data Conventions

Confidence intervals will be calculated at the two-sided 95% level of confidence except for the primary efficacy and safety endpoints which will be one-sided 99% and 95% respectively.

This study is designed to test for non-inferiority of GC5107 which will be compared with historically-based standards. The null hypothesis is that the incidence of serious acute bacterial infections in subjects treated with GC5107 is greater than or equal to 1.0 per subject per year. The alternative hypothesis is that the incidence of serious acute bacterial infections is less than 1.0 per subject per year. Symbolically, this is expressed as follows:

H0: average incidence of serious acute bacterial infections on GC5107  $\geq$  1.0 per subject per year

H1: average incidence of serious acute bacterial infections on GC5107  $<$  1.0 per subject per year

A one-sided test based on a generalized linear models procedure for Poisson regression with  $\alpha=0.01$  will be used to test this hypothesis. Equivalently, the upper one-sided 99% confidence limit would be less than 1.0.

Adverse Event related efficacy endpoint are defined based on treatment emergency adverse event (TEAE) only, including acute serious bacterial infections, infection other than acute serious bacterial infections, incidence of infections, duration of infections, time to resolution of infection.

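### SAP 4.7.3 summarises other infections by trough IgG in two groups split at the cohort mean, which describes the association less precisely than the continuous trough already recorded would

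*SAP*

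**What the plan says.** SAP 2.2 lists the secondary endpoint: "The incidence of infections other than serious bacterial infections by trough IgG levels". The protocol synopsis lists the same endpoint.

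SAP 4.7.3 has two sentences on how trough enters the analysis:

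- First: "The categories of trough IgG levels will be determined by looking at the distribution of trough IgG levels at the study completion". This fixes neither the number of groups nor the cut-points.
- Second: "Incidence will be summarized by total group mean of trough IgG level throughout treatment". The bullet names two groups, below the mean and at or above it. The window for the samples that enter the mean is given as "including the trough IgG level from infusion 1 to follow up assessment".

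On the type of analysis, the section says: "These endpoints will be analyzed descriptively by infusion schedule and overall based on ITT and PP populations, respectively". It names no slope, trend or rate ratio for this endpoint.

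On the data, SAP 2.5 says: "Trough serum total IgG levels before each infusion of GC5107 in all subjects and the interval between infusions will be recorded". A continuous trough series therefore exists for every subject.

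**The concern.** The endpoint asks how infection incidence varies with trough level. A split at the mean treats two subjects just either side of it as opposites, and two subjects far apart on the same side as identical. It gives no estimate of change per mg/dL.

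The cut is also a property of this sample. It is not the 500 mg/dL target that the plan uses elsewhere (SAP 2.6), and SAP 4.7.3 cites no source for it. A two-cell result whose boundary moves with the cohort mean is hard to set beside results from another cohort.

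What is at stake is how well a small study can describe the relation between exposure and infection. The primary efficacy and safety conclusions do not depend on it.

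**Working it through.** The documents give no power, effect size or precision target for this endpoint, so there is no figure of theirs to reproduce. The check is the efficiency of a grouped trough relative to the continuous trough.

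**Inputs from the documents**
- At least 42 subjects (protocol synopsis, study population) and at most 50 (SAP 3: "To guard against dropout and to assure more than adequate power, up to 50 subjects will be enrolled").
- Two groups split at the mean (SAP 4.7.3).
- Continuous trough available before each infusion (SAP 2.5).

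**Assumptions, because the documents give no figures**
- The shape of the trough distribution.
- A log-linear relation between infection rate and trough.
- Each subject is classified by his or her own mean trough. This is the natural reading, but SAP 4.7.3 does not state the unit.

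**Efficiency of the mean split.** The information kept about a linear gradient is the squared correlation between the trough X and the indicator that X is at or above its mean. For a normal X:
- correlation = φ(0)/√(0.5 × 0.5) = 0.3989/0.5 = 0.798
- efficiency = 0.798² = 2/π = 0.637, a loss of 36.3%
- effective size: 42 × 0.637 ≈ 27 and 50 × 0.637 ≈ 32
- interval width for the gradient: 1/√0.637 = 1.25, about 25% wider

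**Other assumed shapes** (by simulation of the same squared correlation; the uniform also has the exact value 0.75):

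| Trough shape | Information lost |
|---|---|
| Uniform | 25% |
| Normal cut off below 500 mg/dL (mean 900, SD 250 before the cut) | 34% |
| Normal | 36% |
| Log-normal, CV 0.2 to 0.5 | 37% to 42% |
| t with 5 df | 46% |
| Log-normal, CV 0.8 | 49% |

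At the ends of this range the interval is 1/√0.75 = 1.15 to 1/√0.51 = 1.40 times as wide.

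**More than two groups** (normal trough, equal groups scored at their means; efficiency is the between-group variance):
- Thirds: outer group mean = 3 × φ(0.431) = 1.091; efficiency = (2/3) × 1.091² = 0.793, a loss of about 21%.
- Quarters: group means ±1.271 and ±0.325; efficiency = 0.5 × (1.271² + 0.325²) = 0.861, a loss of about 14%.

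**Check at the trial's size.** Over-dispersed Poisson regression was simulated with 42 and 50 subjects, 2.5 to 4 infections per subject-year, a rate ratio of 0.7 to 0.8 per SD of trough, and variance 1 to 3 times the mean. All of these values are assumed. The squared ratio of the mean test statistics, split against continuous, was 0.56 to 0.64, a loss of 36% to 44%. The simulated model had no infusion-schedule term.

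**The case against.** The strongest reply is that the endpoint is descriptive by design. SAP 4.7.3 says so, and the protocol synopsis reports descriptively everything beyond the analyses it names. A table of incidence by trough category is a direct reading of an endpoint worded as incidence by trough level. This stands to the extent that nothing in the plan is invalid. It does not make two cells a good description, and the fix adds an estimate without a test or success claim.

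Several stronger readings are tempting, and the documents do not support them:

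- **That the trial loses power.** Under the normal-trough assumption, a continuous analysis with 80% power would have 61% after the split: Φ((1.96 + 0.84) × 0.798 − 1.96). The plan runs no such test, so this describes a hypothetical analysis.
- **That a third of the information is lost as a matter of fact.** The documents give no trough distribution, and entry requires documented troughs of at least 500 mg/dL, which selects from below. The loss is about 36% under stated assumptions, with a range of 25% to 49%.
- **That the loss is the same whatever category rule applies.** The distribution-based sentence in the same bullet could yield three or four groups and a smaller loss. The two sentences need reconciling.
- **That this is the only planned analysis linking exposure to infection.** The contents lists name protocol 9.1.5 and SAP 4.9.2, but their text was not available for review, so this cannot be confirmed.
- **That a continuous model would reveal a true effect of trough.** Subjects keep the dose and interval of their earlier individualised therapy, and SAP 1 links higher doses with chronic sinopulmonary disease. Trough may be confounded with infection risk. This limits the regression and the two-cell table equally.

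Displaying results by infusion schedule adds no detail on trough. It spreads 42 to 50 subjects over four cells, on average 42/4 = 10.5 to 50/4 = 12.5 each.

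**Conclusion.** The point holds as an optional improvement in precision. SAP 4.7.3 reduces a continuous measurement to two groups at a sample-specific cut, and the available text plans no continuous analysis. With a near-normal trough, a log-linear gradient and the two-group rule in force, about 36% of the information on the gradient is lost and its interval is about 25% wider. The size depends on the assumed trough shape and on how many groups are finally used. If risk levels off above some trough, the linear benchmark itself changes. It would be wrong to infer that a planned test is underpowered or that any primary conclusion is affected.

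**What to change.** In SAP 4.7.3, add an over-dispersed Poisson regression, the model class already specified in 4.7.2 and 4.7.4:

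- **Outcome:** each subject's count of infections that are not acute serious bacterial infections.
- **Offset:** log follow-up time, as defined in 4.7.2.
- **Covariate:** the subject's mean on-treatment trough, kept continuous.
- **Report:** the rate ratio per 100 mg/dL with a two-sided 95% interval, the level SAP 4.7.1 already sets outside the primary endpoints ("Confidence intervals will be calculated at the two-sided 95% level of confidence except for the primary efficacy and safety endpoints"). Label it a descriptive association with no success claim.
- **Definitions:** state that the subject is the unit and which visits count. The present window opens with the infusion 1 sample, taken before any GC5107 has been given.
- **Table:** keep the below/above-mean display as support, and reconcile the two category sentences.

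If infusion schedule enters as a factor, add a one-line exception to SAP 4.7.1.2, which says covariate adjustment does not apply.

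The cost is SAP wording and one model on data already collected; visits, sampling, sample size and primary analyses are unchanged. Two limits should be stated: the model assumes log-linearity, which a plot of infection rate against trough can check, and the association may be confounded by individualised dose and interval.

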4.0	Date of last signature	
 
• Added imputation rule for partial first lifetime IGIV infusion date.
 
• Added imputation rule for missing or partial AE start date, when analyzing the yearly duration of infections.
 
• Clarify the definition of infections in section 4.7.3.
 
• Added Protocol Version 2, Amendment 1 REB Approval Dates to Appendices.
 
• Section 4.7.3, add clarification of handle subject with no experience of event.
 
• Section 4.4.3, add clarification of trough IgG level categorization.
 
• Added Section 4.7.4 Exploratory Efficacy Variable
 

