### Investigators and Study Centers

---

[REDACTED]

[REDACTED]

[REDACTED]

A sufficient number of study sites to enroll up to 50 subjects to obtain at least 26 adult subjects, at least 8 adolescent subjects and at least 8 child subjects will be recruited. Subjects who withdraw (or are withdrawn) will not be replaced.

Randomization and Stratification

Not applicable.

Blinding

Not applicable.

Treatment Regimens

All subjects will receive intravenous infusions of investigational product at the same dose and interval as used for their previous IGIV maintenance therapy. GC5107 will be administered at a dose of 300 - 900 mg per kg (of body weight) every 21 or 28 days ( $\pm 4$  days) for a period of 12 months.

Visit Schedule

The Table 1 below summarizes the timeline for the study. For detailed visit schedule, please refer to the study protocol for GC5107B\_P3 (Section 5.8).

Table 1: Study Timeline

Procedure 28 day regimen (21 day regimen in parentheses)	Time	
Screening*	Day -28 to Day -1 (Day -21 to Day -1)	Up to 28 days prior to the first infusion
Infusion 1	Week 0, D1 Baseline	12 months of infusions
Infusion 2-4 (Infusion 2-4)	Week 4 – 12 (Week 3-9)	
PK Assessment Infusion 5 (Infusion 5)	Week 16 (Week 12)	
Infusion 6 – 13 (Infusion 6 - 17)	Week 20 – 48 (Week 15- 48)	

Follow-up: 4 weeks after last infusion (3 weeks after last infusion)	Week 52 (Week 51)	3 or 4 weeks after the last investigational product infusion
--	----------------------	--

Note: The screening procedures can occur only after a potential subject has signed the ICF. Results of screening must be obtained before the first study infusion.

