### 4.2 General Presentation Considerations

‘Baseline’ is defined as the last available pre-treatment assessment, unless specified in later section. ‘End of Study’ is defined as the last available post-treatment assessment. ‘Treatment Day’ will be calculated relative to the date of the first infusion of GC5107, i.e. Treatment Day = Assessment Date - First Infusion Date + 1 (if on or after day of first infusion); or Treatment Day = Assessment Date - First Infusion Date (if before day of first infusion).

Continuous data will be summarized in terms of the mean, standard deviation (SD), median, minimum, maximum and number of observations, unless otherwise stated. Continuous data that are expected to be skewed will be presented in terms of the maximum, 75% quantile, median, 25% quantile, minimum and number of observations. The minimum and maximum will be reported to the same number of decimal places as the raw data recorded in the database. The mean, median, lower quartile and upper quartile will be reported to one more decimal place than the raw data recorded in the database. The SD will be reported to two more decimal places than the raw data recorded in the database. In general, the maximum number of decimal places reported shall be four for any summary statistic.

Categorical data will be summarized in terms of the number of subjects providing data at the relevant time point (n), frequency counts and percentages. . Any planned collapsing of categories will be detailed in the SAP text and the data displays.

Percentages will be presented to one decimal place. Percentages will not be presented for zero counts. Percentages will be calculated using N as the denominator unless otherwise indicated. If sample sizes are small, the data displays will show the percentages, but any textual report will describe frequencies only.

Changes from baseline in categorical data will be summarized using shift tables where appropriate. For continuous variables, actual values and changes from baseline will be summarized using descriptive statistics across infusion schedule and overall by visit.

P-values greater than or equal to 0.001, in general, will be presented to three decimal places. P-values less than 0.001 will be presented as “<0.001”.

Confidence intervals will be presented to one more decimal place than the raw data.

All report outputs will be produced using SAS® version 9.3 or a later version in a secure and validated environment.

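### Time to resolution of infections is planned as a simple descriptive summary with zeros for infection-free subjects and no visible censoring rule, which understates it, modestly if infections are short

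*SAP*

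**What the plan says.** SAP 4.7.3 names "Time to resolution of infections" as a secondary efficacy endpoint. The method for the whole list is "These endpoints will be analyzed descriptively by infusion schedule and overall based on ITT and PP populations, respectively".

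SAP 4.2 supplies the default statistics: "Continuous data will be summarized in terms of the mean, standard deviation (SD), median, minimum, maximum and number of observations, unless otherwise stated". For data expected to be skewed it uses quartiles, median and range instead.

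The same paragraph of 4.7.3 adds: "Subject with no experience of specific event will be included in the analysis as zero incidence, zero day, or zero time duration". An infection is a treatment-emergent adverse event: "Infections is defined as TEAE coded to MedDRA system organ class" for infections and infestations, or an event judged to be an infection on medical review.

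Observation ends at week 52 on the 28-day schedule and week 51 on the 21-day schedule (SAP section 3, Table 1). Subjects who withdraw are not replaced. SAP 4.7.2 defines the end of follow-up as the last visit for completers and the withdrawal date for the others, but only for the primary event rate.

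The revision history for version 4.0 records one date rule for infections: "Added imputation rule for missing or partial AE start date, when analyzing the yearly duration of infections". The rule itself is not in the available text.

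**The concern.** Time from onset to resolution is a time-to-event quantity. An infection open when observation stops has a known minimum length but no known end. A plain mean or median needs a number for every infection, so an open one must be left out or given its observed length as if it had resolved. Both shorten the result, because long infections are the ones most likely to be open. These persistent infections are the unfavourable outcome that the endpoint should show.

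The zero rule pulls the same way. A subject who never had an infection has no time to resolution. Entering zero treats absence of infection as instant recovery. It also turns a measure per infection into a measure per subject that mixes how often infections occur with how long they last.

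**Working it through.** The documents give no expected duration, number of open infections or precision for this endpoint, so there is no planned figure to reproduce. The check asks how far simple summaries fall short under stated assumptions.

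**Inputs**
- Follow-up T: 364 days (52 × 7) or 357 days (51 × 7), from SAP Table 1. T = 182 days stands for a half-year withdrawal (assumed).
- Mean duration m: 7, 14, 30 and 60 days (assumed), exponential or lognormal with log-SD 1.
- Onset: uniform over follow-up (assumed).

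**Formulas, exponential case**
- Share still open at T: p = (m/T)(1 − exp(−T/m)).
- Mean if open infections are cut at T: m(1 − p), so the relative shortfall equals p.
- Mean if open infections are dropped, for T much larger than m: about (m − 2m²/T)/(1 − m/T).

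**Worked case, m = 14, T = 364**
- p = 14/364 = 3.8%.
- Cut: 14 × (1 − 0.0385) = 13.46 days.
- Dropped: (14 − 2 × 196/364)/(1 − 0.0385) = 12.92/0.9615 = 13.44 days, or 4.0% low.

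**Simulation, 1,000,000 infections per setting.** Ranges run from exponential to lognormal.

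| T (days) | m (days) | open | shortfall in mean, dropped | shortfall in mean, cut |
|---|---|---|---|---|
| 364 | 7 | 2% | 2.0-3.3% | 1.9-2.6% |
| 364 | 14 | 4% | 4.0-6.8% | 3.8-5.2% |
| 364 | 30 | 8% | 8.9-14.0% | 8.2-10.9% |
| 364 | 60 | 16% | 19.5-25.5% | 16.4-20.3% |
| 182 | 14 | 8% | 8.4-13.1% | 7.7-10.2% |

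T = 357 gives almost the same values as T = 364.

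**Medians.** For m = 14, T = 364, exponential, the true median is 9.71 days. Dropping gives 9.32, cutting gives 9.34, and Kaplan-Meier with open infections censored gives 9.71. Kaplan-Meier was within 0.1 day of the truth in every setting. In the simulation, censoring is unrelated to duration.

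**Weight of early leavers.** Suppose 8 of 50 subjects leave at 90 days (assumed; the protocol synopsis enrols up to 50 to obtain at least 42). They contribute 8 × 90 = 720 days against 42 × 364 = 15,288, which is 720/16,008 = 4.5% of follow-up. With open infections dropped and exponential durations, the pooled mean moves from 13.44 to 13.36 days at m = 14, and from 48.4 to 47.7 days at m = 60.

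**Zero rule.** Subject-level mean = (share of subjects with an infection) × (mean among those infected). If that share is 90%, 80%, 70% or 50% (assumed), the mean falls by 10%, 20%, 30% or 50%. If half or more of the subjects have no infection, the median is zero.

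**The case against.** The strongest objection is that silence in 4.7.3 is not silence in the plan. SAP 4.7.1.3, on dropouts and missing data, is only a heading in the copy reviewed. SAP 4.8.3 on adverse events and the protocol sections on secondary efficacy (6.2 and 9.1.5) are also absent. Protocol section 8, which may say whether open events are followed to resolution, is absent too. This stands. A reader might infer that the SAP has no censoring and that open infections will be dropped or cut, but no available text states either.

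A reader might also infer from the revision history that only start dates are imputed. A log of what version 4.0 added cannot show that no stop-date rule existed before. The entry concerns the yearly duration of infections, which may be a different measure, since SAP 4.7.1 lists duration and time to resolution separately. If it is an annualized per-subject quantity, cutting both infection days and follow-up at the same date is ordinary person-time accounting.

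The objection that the effect is small also stands in part. At 7-14 days it is a few percent, and the endpoint has no test or success criterion. The PP population contains only 12-month completers, so truncation at withdrawal cannot occur there. Equally, infections open at withdrawal can be seen only in ITT.

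The objection does not rescue the stated method. A plain descriptive summary is not a censored analysis, and a rule that filled in the last-contact date as the stop date would still truncate. The zero rule is written in 4.7.3 and needs no inference.

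**Conclusion.** The concern holds in limited form. As written, SAP 4.7.3 gives time to resolution a simple descriptive summary and enters infection-free subjects as zero time, with no censoring rule in the available text. If open infections are dropped or cut, the mean over a full year is about 2-7% too low for mean durations of 7-14 days and about 16-26% too low for 60 days. The zero rule could matter more: 10-50% if 90% down to 50% of subjects have an infection. All these sizes rest on assumed durations, uniform onset and assumed infection shares.

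The larger losses in early leavers should not be read as the size of the error for the trial, because such subjects carry little weight in the pooled summary. Nor do the documents support a reading that the efficacy conclusion is at risk: the primary endpoint is a rate of serious bacterial infections and does not use this summary. This is a cheap improvement to a secondary endpoint.

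**What to change.** In SAP 4.7.3:

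1. Summarize time to resolution per infection by Kaplan-Meier, from onset to resolution, censored at the end-of-follow-up date defined in SAP 4.7.2 (last visit or withdrawal). Report the median and quartiles by infusion schedule and overall, for ITT and PP.
2. State that the zero-duration rule does not apply to this summary.
3. Report the number of infections unresolved at withdrawal and, separately, at study end. Kaplan-Meier assumes that censoring is unrelated to remaining duration, which may fail when an infection caused the withdrawal. The counts make such cases visible.
4. If 4.7.1.3 already sets a censoring rule, cross-reference it here.

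The cost is a few lines of SAP text and one standard procedure using infection start and stop dates. Reported times may be slightly longer. A subject can contribute several infections, so the curve is descriptive only. If infections prove short and withdrawals few, the unresolved counts alone would give most of the benefit.

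### SAP section 4.7.3 does not exempt time to resolution of infections from its zero rule, so infection-free subjects would enter as 0 days and shorten the summary

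*SAP*

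**What the plan says.** SAP section 4.7.3 lists nine secondary efficacy endpoints: two incidences, six day counts, and "Time to resolution of infections". The paragraph below the list opens: "These endpoints will be analyzed descriptively by infusion schedule and overall based on ITT and PP populations, respectively". The next sentence is the zero rule: "Subject with no experience of specific event will be included in the analysis as zero incidence, zero day, or zero time duration". No endpoint is excepted.

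The sentence after that concerns hospital stays: "For hospitalizations, the number and (total) duration for each subject will be calculated and converted to a figure per year". The paragraph closes with the standard summary set, "except that the mean and SD will be calculated weighting for the duration of data available for each subject".

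Three other places bear on the reading:

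- SAP section 4.2 sets the default summary: "Continuous data will be summarized in terms of the mean, standard deviation (SD), median, minimum, maximum and number of observations, unless otherwise stated". For data expected to be skewed it substitutes a set of quantiles with minimum, maximum and number of observations.
- SAP section 4.7.1, naming the efficacy endpoints built on treatment-emergent events, lists "incidence of infections, duration of infections, time to resolution of infection" as separate items.
- The version 4.0 entry in the SAP revision history mentions an imputation rule for adverse event start dates, used "when analyzing the yearly duration of infections".

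**The concern.** A subject with no infection truly has zero infections, zero days of antibiotics and zero days in hospital. The same subject has no time to resolution at all. A 0 entered there is not an observation of the endpoint; it reads as an infection that resolved at once.

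With those zeros in, the summary mixes two quantities: how many subjects had an infection and how long infections took to clear. It shortens as more subjects stay infection-free, even if no infection resolves any faster. A reader of the table could not tell fewer infections from quicker recovery, and the error runs in the product's favour. With subjects as the unit, the number of observations would also be the whole ITT or PP population and not those who had an infection.

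**Working it through.** **Which endpoints the rule reaches.** Its three kinds of zero match the three kinds of endpoint in the list. Zero incidence fits the incidence endpoints and zero day fits the day counts, hospital days included. Zero time duration is left for time to resolution, the only listed endpoint expressed as a time. Where the SAP wants an annualised total it says so, for hospital stays (section 4.7.3) and for fever (section 4.7.4). It does not say so for time to resolution.

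**Inputs.** The documents state no infected share, infection rate or resolution time, so there is no figure of the plan's own to reproduce.

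- From the plan: minimum sample 26 + 8 + 8 = 42 subjects (SAP section 3).
- Assumed: a true mean of 10 days to resolution among those infected, and the infected shares and infection rates shown below.

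**(a) Unweighted mean, subjects as the unit.** Let *p* be the share of subjects with at least one infection. Reported mean = *p* × 10.

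| Infected | Reported mean (days) |
|---|---|
| 70% | 7.0 |
| 80% | 8.0 |
| 90% | 9.0 |
| 34 of 42 (8 infection-free) | 8.1 |
| 40 of 42 (2 infection-free) | 9.5 |

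Two different situations give the same figure. With 20% infection-free and 10-day infections, 0.8 × 10 = 8.0 days. With 50% infection-free and 16-day infections, 0.5 × 16 = 8.0 days.

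**(b) Mean weighted by follow-up, if that weighting reaches this endpoint.** Let *w* be the follow-up of infection-free subjects relative to infected subjects. Factor = *p* / (*p* + (1 − *p*)*w*). At *p* = 0.80:

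- *w* = 1: 0.80/1.00 = 0.80, or 8.0 days
- *w* = 0.75: 0.80/0.95 = 0.84, or 8.4 days
- *w* = 0.5: 0.80/0.90 = 0.89, or 8.9 days

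**(c) Infections as the unit, with one zero row per infection-free subject.** With a Poisson rate of *L* infections per subject-year and one year of follow-up, factor = *L* / (*L* + e^−*L*). The matching subject-level share is 1 − e^−*L*.

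| *L* | Per-infection factor | Subject-level share |
|---|---|---|
| 1 | 0.73 | 0.63 |
| 2 | 0.94 | 0.86 |
| 3 | 0.98 | 0.95 |

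**(d) Minimum and quantiles, subjects as the unit.** With at least one infection-free subject the minimum is 0 under either summary set in SAP section 4.2; this needs no assumption about the share. The quantiles shift too. At 20% infection-free the reported median is the (0.50 − 0.20)/0.80 = 37.5th percentile among infected subjects. Above 50% infection-free the median is 0.

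**The case against.** The strongest reply is that the phrase about zero time duration was never aimed at time to resolution. The next sentence of section 4.7.3 speaks of yearly hospitalization duration, and the revision history for the same SAP version mentions a yearly duration of infections. Zero is correct for both. The SAP also turns event durations into yearly totals for hospital stays and fever. Time to resolution may have been meant the same way, and then only its label is loose. The argument adds that the rule speaks of duration: if section 4.7.1 treats duration and time to resolution as different things, the rule names the other one. Finally, the body of SAP section 4.7.1.3 and of Protocol section 9.1.5 was not in the text available for this check, and either could define the endpoint or its unit.

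Part of this stands. The yearly-total reading is possible, and the unseen sections could settle it. But section 4.7.3 does not state that reading, and section 4.7.1 lists the two quantities separately. The general wording also applies the rule to every listed endpoint, so a programmer following it would enter the zeros.

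It is also fair that every size above rests on assumed inputs, that (b) and (c) describe outputs the plan does not clearly call for, and that a quantile summary would carry no mean. The zero minimum and the shifted quantiles remain in that case. There is no comparator arm in which a differential bias could arise, and no test or decision rule uses this endpoint. That limits the importance of the point without making the rule right.

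**Conclusion.** The point holds for section 4.7.3 as written: the zero rule covers an endpoint for which zero is not a possible observation, and applying it understates time to resolution.

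In the scenarios worked, the reported mean is between 0.63 and 0.98 of the true value. It is about 0.8 at 80% infected when follow-up is equal and subjects are the unit, and close to 1 when nearly all subjects have an infection. These factors depend on assumed infected shares and infection rates; the day figures also assume a 10-day true mean. The zero minimum needs only one infection-free subject.

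The consequence is confined to one descriptive secondary endpoint. The primary efficacy test, its alpha and the sample size are untouched. It should still be corrected, because a stated rule gives a wrong summary, in the product's favour, and the repair is simple. The conclusion would change only if a section not seen here defines the endpoint as a yearly total; the label would then be what needs correcting.

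**What to change.** In SAP section 4.7.3:

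1. Limit the zero rule to incidence, day-count and total-yearly-duration variables, including yearly hospitalization duration.
2. Summarise time to resolution only among infections, or only among infected subjects. State which unit is used, and report the number of infection-free subjects alongside.
3. If a total yearly duration of infection is what is intended, name the endpoint as that and keep the zeros for it.

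Before redrafting, check SAP section 4.7.1.3 and Protocol section 9.1.5 for an existing definition and align the wording with it. The cost is a change of SAP wording and one table shell. No new data are needed.
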